Population:	Adolescent sexual minority males ($N = 150$, male sex, male gender identity, 14-17 years old; self-identify as gay/bisexual, report being sexually attracted to males, or report having voluntary sexual contact with a male partner in the past year)
Intervention:	Online sexual health media literacy intervention
Objectives:	The objective of this pilot study is to assess the acceptability, feasibility, and preliminary efficacy of an online sexual health media literacy intervention
Design/Methodology:	A RCT design with two conditions (i.e., online sexual health media literacy vs. control) and three assessments (i.e., baseline, post-intervention, 3 month follow-up). See Appendix 1 for detailed study flow diagram.
Total Study Duration:	24 months
Subject Participation Duration:	3 months

3 Background/Rationale & Purpose

3.1 Background Information

Adolescent sexual minority males (ASMM), ages 14-17, are disproportionately affected by HIV in the United States (US).¹ Racial and ethnic minority ASMM are particularly affected.² The disproportionate incidence among ASMM is largely attributed to engagement in sexual risk behaviors, including condomless anal intercourse (CAI).^{3,4}

Despite increased risk, few HIV prevention interventions target ASMM < 18 years old.^{5,6} For ASMM, adolescence (ages 14-17) is a developmental period when significant biopsychosocial changes are coupled with negotiation of a same-sex attraction.^{4,7-11} Further, ASMM are particularly susceptible to perceived peer norms, including media-based perceived norms,^{12,13} which predict behavior.^{9-11,14} As most sexual risk behavior patterns are established during adolescence among ASMM,^{3,4,15,16} it is important for HIV prevention interventions to target ASMM during this vulnerable period. Intervening with ASMM will help them learn and establish healthy sexual behaviors,⁴ which will have both immediate and long-term health benefits.^{4,15,17,18}

The CDC has highlighted the importance of addressing online media influences on HIV risk among adolescents.¹⁹ One Internet source that contributes to ASMMs’ HIV risk is their use of sexually explicit online media (SEOM; i.e., online pornography).^{20–26} With limited access to relevant sexual education in school^{27–29} or from parents,²⁴ ASMM use SEOM^{20–26,30} and adopt the behaviors they see.^{23,26}

The amount of male-male specific SEOM portraying CAI has increased substantially in recent years,^{31,32} raising concerns about the encouragement of risky sexual behaviors among consumers.^{33,34} 105 These concerns are supported by five large-scale studies showing positive associations between exposure to CAI in sexually explicit media and engagement in CAI among adult MSM^{35–39} and one among ASMM.²⁶ Further, ASMM report modeling their sexual experiences after what they view in SEOM, including engaging in CAI.^{23,26}

As SEOM triggers and maintains sexual risk-taking among ASMM,^{20–26,30} it is critical for HIV prevention interventions to address the influence of this “super peer.”^{12,13,25} One way to address this influence is by developing a SEOM-targeted sexual health media literacy intervention.^{12,25,40} Media literacy interventions have positively impacted many health behaviors,⁴¹ including sexual health behaviors,^{42–44} and may be an effective means of addressing the influence of SEOM on the sexual risk of adolescent ASMM. As such, using information from an online survey of ASMM from across the US^{24,26,45,45–47} and the guidance of a youth advisory board, we developed an online sexual health media literacy intervention called the Young Men & Media (YM&M) intervention.

The procedures involved in this research (i.e., online assessments, online intervention) are considered low-risk. Thus, participants will incur minimal risks due to their participation in this study. This study will be conducted in compliance with the protocol, applicable regulatory requirements, and BMC/BU Medical Campus Human Research Protection policies and procedures.

3.2 Rationale and Purpose

Given ASMMs’ increased risk for HIV¹ in combination with their decreased access to relevant sexual health education from traditional sources^{24,27–29} and reliance on SEOM for sexual health information,^{20–26,30} development of sexual health interventions for ASMM that address male-male sexual practices and SEOM are critical. To our knowledge, YM&M is the first intervention to specifically address SEOM use among ASMM. To ensure that this approach is both feasible and acceptable to ASMM we are proposing to pilot test the intervention.

4 Objectives

4.1 Study Objectives

The goal of this study is to conduct an exploratory clinical trial to pilot test the online media literacy intervention for feasibility, acceptability, and preliminary efficacy.

4.2 Study Outcome Measures

An overview of outcome measure timing is provided in Table 1.

4.2.1 Primary Outcome Measures

The **primary outcomes** will be feasibility and acceptability of the intervention.

Feasibility measures. To assess study feasibility, banner ad click-through rate, number of individuals recruited per week, and the percentage of individuals who were eligible; assented; dropped out and lost to follow-up will be calculated. To assess the feasibility of the media literacy

Purpose	Construct or Behavior	Baseline	Intervention	Post Intervention	Follow-up
Feasibility	Study recruitment	x			
	Study retention			x	x
	Intervention metrics		x	x	
Acceptability	Webpage ratings		x		
	Satisfaction survey			x	
Preliminary Efficacy	Sexual risk behaviors	x			x
	Antecedents to sexual risk	x		x	x
	Media literacy	x		x	x
	Sexual health knowledge	x		x	x

intervention we will calculate intervention metrics (i.e., time spent on each piece of intervention content, percentage who complete all intervention content).

Acceptability measures. To assess acceptability, media literacy intervention participants will be asked to complete content ratings on each piece of intervention content using a 5-star rating system. Participants will also be given the option of providing written feedback on each piece of content as well. All participants will also be asked to complete a satisfaction survey at the post-intervention follow-up.⁴⁸ Participants will be asked to report on study procedure acceptability (e.g., acceptability of recruitment, consent, assessment procedures). Intervention participants will be asked to report how informative, interesting, and helpful the intervention was; how likely they would be to recommend it to friends; and if they have suggestions for how it could be improved. Participants in the control group will be asked which website they went to, if any, and to report how informative, interesting, and helpful the website was; as well as how likely they would be to recommend it to friends. The satisfaction survey will include a combination of likert scale and open-ended responses.

4.2.2 Secondary Outcome Measures

The **secondary outcomes** will measure preliminary efficacy (i.e., changes in sexual risk behaviors, media literacy skills, and sexual health knowledge).

Sexual risk. Sexual risk behaviors and antecedents to sexual risk behaviors will be assessed. Participants will be asked about the number of sex partners, gender of partners, HIV-status of partners, romantic/primary partner status, sexual activities and condom use, and substance use with sex in the prior 3 months. Participants will be asked to report only on voluntary sexual behavior (i.e., not forced). To optimize the accuracy of these reports, counts of behaviors will be asked in an open response format.^{49–52} Antecedents to sexual risk-taking include intentions to have sex and for sexual communication (e.g., communication about HIV/STI status, condom use)^{44,53} as well as condom attitudes.⁵⁴

Media literacy skills will be assessed using questions adapted from the two previous sexual health media literacy interventions, including awareness of SEOM myths, awareness of SEOM influence, and SEOM skepticism.^{42–44}

Sexual health knowledge will be determined by assessing HIV⁵⁵ and STI⁵⁶ transmission knowledge; HIV/STI prevention method knowledge;⁵⁷ and the levels of HIV/STI transmission risk (low, medium, high) associated with sexual behaviors (e.g., oral sex, anal sex).⁵³

5 Study Design

The study design is a pilot randomized controlled trial (RCT) with two conditions (i.e., YM&M intervention vs. control) and three online assessments (i.e., baseline, post-intervention, 3 month follow-up). Prior to randomization all participants ($N = 150$) will complete a baseline assessment. Participants will then be randomly assigned (1:1 randomization) to the intervention or to the control group. The randomization schedule will be generated using a permuted block randomization procedure with small, random-sized blocks. Following receipt of the intervention or control, participants will be asked to complete a post-intervention assessment and a 3-month follow-up. Data will include self-report and usage data. See Appendix 1 for a schematic of the study design and participant flow and Appendix 2 for a schedule of events.

6 Potential Risks and Benefits

6.1 Risks

The procedures involved in this research (i.e., online assessments, online intervention) are considered low-risk. Thus, participants will incur minimal risks due to their participation in this study. Potential untoward events that may occur include:

- Emotional discomfort.
- Breach of confidentiality.

The level of risk for each of these events is minimal.

Emotional discomfort. Some of the topics that are asked about or discussed (e.g., SEOM use, sexual behaviors) may cause discomfort or anxiety. There is also the potential for anxiety related to acknowledging behavior with potential legal implications (alcohol/drug use, condomless sex which placed someone at risk of contracting an infectious disease).

These risks are recognized. Nonetheless, recent research assessing the psychological impact of similar questions among LGBT adolescents found that 90% of the participants reported feeling “very comfortable” or “comfortable” with the questions they were asked and only 3% reported feeling “very uncomfortable,” which is similar to what has been found in other research assessing reactions to questions about sexuality and substance use.^{58,59}

To minimize the potential for participant psychological distress or discomfort during the online assessments and intervention participants will be notified that they can skip any questions or intervention content that they are uncomfortable with and stop the assessment or intervention at any time. Participants will also be invited to contact the PI should any discomfort arise.

Breach of confidentiality. The study will take every precaution to ensure that the privacy of study participants is protected. To guard confidentiality, each participant will receive a unique ID number. All computer records will be protected by standard measures that limit data access to authorized personnel. Online data will be collected and managed using the REDCap⁶⁰ electronic data capture tools managed by Boston University Medical Campus IT. REDCap is a secure, web-based application designed by network engineering and approved by IT Security. REDCap servers are backed up daily and monitored for hardware failures. Self-report and usage data will be collected from respondents, and likewise retrieved by the PI, over an SSL encrypted connection.

The intervention website is designed and implemented by LongTek, Inc., a technology provider with extensive experience creating secure, encrypted websites for research projects. All data (e.g., email addresses, content ratings, time spent on intervention content, number of log-ins) will be housed, monitored, and downloaded by the PI from the PI portal within the intervention website. The intervention website data is protected with SSL in transit via TLS 1.2 using 256 bit RSA encryption. Certain fields within the intervention database (including participant and administration user's emails and passwords) are encrypted at rest using hashed and salted SHA256 bit encryption. Participant data can only be accessed by the specific participant by entering a username and password via the participant login page. The PI login portal has a logically separated data table and dedicated login page that allows PI users access to a real-time view of aggregate data regarding time spent on intervention pages and number of log-ins. The log-in page will not indicate the content, purpose, or target population. Website servers are housed in a highly secure environment, backed up daily (nightly backup of database and file system retained for at least 7 days), and monitored for hardware failures (99.9% uptime).

Participants will be encouraged to go to a private location at the beginning of the survey, assessments, and when they log into the intervention. To mitigate the chance of another person seeing that the participant is in this study, a time limit will be set on the intervention such that if no movements have occurred on the participant's screen within 20 minutes the screen will be redirected to the log-in page. Lastly, all correspondence with participants will be devoid of any indication of the content, purpose, or target population of the study and participants will be encouraged to delete correspondence (e.g., emails) as soon as the participant decides they no longer need the contained information.

In addition, because of the potentially sensitive nature of the data that are being collected, we have received a Certificate of Confidentiality to ensure that participants' data cannot be subpoenaed with a court order. No individual identities will be used in any reports or publications.

Other considerations: Mental health and substance use. As mental health and substance use issues are prevalent among ASMM, we will provide all participants with links and phone numbers for LGBT-specific services (e.g., the National Alliance on Mental Health LGBTQ website, PRIDE Institute Substance Use Treatment website, GLBT National Youth Talkline phone number, Trevor Helpline Crisis Intervention for LGBTQ Youth phone number). Although none of the proposed measures specifically ask about reportable issues, the satisfaction survey for the intervention will include open-ended responses. The PI will check these open-ended responses daily in the unlikely event that a participant reports any indication of current, ongoing abuse or neglect of children or elders and/or of imminent danger to self or a specified individual as these indications will have to be considered for clinical intervention and mandated reporting to the appropriate authorities. Daily checks will be documented via PI initials on a study calendar.

Other considerations: Website developer training. To ensure the website developer is informed of research ethics and participant confidentiality they have completed on-line CITI Human Subjects Protection training and signed an

agreement to keep all participant information confidential. The developer has a background in designing/programming websites for research purposes, thus have completed these trainings and signed research confidentiality agreements before.

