- **Recruitment, screening, and assent (described in more detail below):** Participants will be recruited via online advertisements. Once they click on an advertisement they will be presented with information about the study and a brief online screener to establish eligibility. If they are eligible they will be presented with assent materials and complete capacity to assent questions. If they agree to participate they will then be emailed a unique link to the baseline assessment.
- **Baseline assessment:** Participants will be sent an email with a link to a self-report online survey ($N = 150$; Approx. 25-35 minutes); compensation for time (\$15 electronic gift card via email). If participants do not complete the baseline assessment within three days of assenting, we will send them up to 3 reminder emails in a 10-day period.
- **Randomization:** immediately following the final question in the baseline assessment, REDCap⁶⁰ will be programmed to randomly assign participants (1:1 randomization) to the YM&M intervention or to a control group. The randomization schedule will be generated using a permuted block randomization procedure with small, randomized blocks.
 - Participants randomized to the YM&M ($n = 75$) intervention will be sent an email with username (their email) and a temporary password and asked to complete all of the website content within three weeks of receiving the email. Participants will be asked at first log-in to set up their own password. If a participant has not logged into the website within one week of receiving the original email, they will be sent up to 3 reminder emails in a 10-day period.
 - Participants in the control condition ($n = 75$) will be sent an email with links to various HIV prevention websites (e.g., the CDC HIV Prevention site, the National HIV and STD Testing Resource site) and encouraged to visit at least one site in the next three weeks.
- **YM&M intervention exposure:** Intervention content, language, and length was informed by a youth advisory board and a previously completed online survey.^{24,26,45,45-47} Although the intervention is designed to be completed in one sitting (i.e., < 90 minutes in length), participants will be given the option of logging out and logging in again to continue where they left off, should they need to. Intervention content is described in more detail above and in Appendix 3.

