11.1 Confidentiality

Confidentiality of study data will be maintained by numerically coding all data, by disguising identifying information, and by keeping all data in password-protected, encrypted computer files. All information obtained from participants will be accessible only to research staff. Study staff will maintain participant privacy by securing records using password-protected, encrypted databases. In meetings when study procedures are reviewed and issues of compliance are raised, participants will not be identified by name unless necessary, and if necessary only by first name. Project meetings will be held in private conference rooms.

Data will be obtained from electronic assessments completed by study participants and usage data from the study website. Personally identifiable information (PII), assessment responses, and usage data will be kept in separate datasets. They will be linked only with a randomly generated ID variable that is included in all data. Although the datasets will be housed on the same server (e.g., REDCap for assessment and self-report data, the intervention website for usage data and content review data), they will otherwise be completely separate. The PII dataset will be deleted upon completion of data collection and cleaning. AE reports and annual summaries will not include subject-identifiable material. Multiple levels of password protection will be utilized and access will be denied to non-study personnel. No identifiable information will be stored on laptops or transportable devices in this study. Further, REDCap and website servers will be physically stored in high security areas and study desktops will be located within a secured building.

If it is discovered that despite security precautions electronic data has been hacked, or if someone has illegally gained access to any data, the PI will determine to what extent the hacking has been successful. The PI will promptly inform the appropriate authorities to the extent of the hacking (e.g., BU, the IRB, NIH project officer, and, if appropriate, the police department). The PI in collaboration with the above authorities will determine what action, if any, is appropriate. In the unlikely event that hacking occurs, an attempt will be made to contact every participant potentially affected by the hacking to inform them that their data may have been accessed. Legal recourse will also be sought to

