11.2 Source Documents

There are two sources of data: (a) participant self-report and (b) usage data:

- **Self-report data:** will be collected via content ratings for each piece of intervention content and the assessments. Assessments for the pilot RCT will be conducted at baseline, post-intervention (3 week after baseline), and follow-up (15 weeks after baseline). Assessment data will be collected using a secure online survey software system, namely, REDCap.⁶⁰ Content ratings will be collected through the intervention website.
- **Usage data:** will include banner ad click-through rate, time spent on intervention content, and number of intervention website log-ins. Banner ad click-through rate will be acquired from the advertising websites. Time spent on each piece of intervention content and number of intervention website log-ins will be collected via the intervention website.

Only authorized study personnel will have access to the data.

Self-report measures. An overview of the constructs and assessed behaviors is provided in Table 3.

Descriptive measures and moderators.

Socio-demographics. Age, race/ethnicity, birth sex, gender identity, sexual orientation, education level, living situation, and zip code will be asked using standard formats. **Legal Guardians.** Participants will be asked questions about their legal guardians and how “out” they are about their sexual attraction to male partners.¹⁵ **Outness.** Participants will also be asked about their overall degree of “outness.”^{37,87} **Healthcare access/use.** Access and use of healthcare services, including HIV/STI testing.⁷⁷ **Substance use.** The impact of participants’ use of alcohol and other drugs will be assessed using the CAGE Adapted to Include Drugs (CAGE-AID).⁸⁸ Participants will also be asked about which drugs they used recreationally in their lifetime. **Mental Health**

Table 3. Measures: Purpose and Timing of Administration

Purpose	Construct or Behavior	Baseline	Intervention	Post Intervention	Follow-up
Descriptors / Moderators	Socio-demographics	x			
	Legal Guardians	x			
	Outness	x			x
	Healthcare access/use	x			x
	Substance Use	x			x
	Mental Health	x			x
	Sexual Abuse History	x			x
	Sexual Education Exposure	x			x
Feasibility	Study recruitment	x			
	Study retention			x	x
	Intervention metrics		x	x	
Acceptability	Webpage ratings		x		
	Satisfaction survey			x	
Exposure	SEOM exposure	x			x
Mediators	Identification with SEOM actors	x		x	x

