12.3 Statistical Methods

Because this is a small pilot study, analyses are not powered to detect intervention effects or formally test mediation or moderation. To determine feasibility of conducting a RCT, we will calculate the percentage of individuals who were: eligible; assented; were randomized; and completed the post-intervention and 3-month follow-up. To determine feasibility of the intervention, we will calculate the total time spent on each intervention page as well as the percentage of individuals who complete the intervention. To determine acceptability of the intervention, we will calculate mean content ratings for the intervention pages and satisfaction surveys as well as inspect open-ended responses. As a secondary goal and to obtain preliminary evidence of efficacy of the online media literacy intervention, we will examine the within- and between-group differences at each follow-up for all three efficacy measures (i.e., sexual risk, media literacy, sexual health knowledge) using a series of longitudinal mixed effects models, controlling for baseline values, as well as any group differences.

13 Ethics/Protection of Human Subjects

This study is to be conducted according to applicable US federal regulations and institutional policies (which are based in federal regulations, guidance, and ICH Good Clinical Practice guidelines).

This protocol and any amendments will be submitted to the Boston Medical Center and Boston University Medical Campus IRB, for formal approval of the study conduct. The decision of the IRB concerning the conduct of the study will be made in writing to the investigator. A copy of the initial IRB approval letter will be provided to NIMH before commencement of this study.

All subjects for this study will be provided assent material describing this study and providing sufficient information for subjects to make an informed decision about their participation in this study. The assent material will be submitted with the protocol for review and approval by the IRB. The assent of a subject, using the IRB-approved assent material, must be obtained before that subject is submitted to any study procedure. Assent will be documented as required by the IRB.

14 Literature References

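### Does the wording on access to the intervention-website data leave the completion percentage impossible to calculate?

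*Combined protocol and SAP*

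**What the plan says.** - **Outcome.** Section 4.2.1 makes feasibility and acceptability the primary outcomes. The intervention metrics include the "percentage who complete all intervention content". Section 12.3 repeats this: "we will calculate the total time spent on each intervention page as well as the percentage of individuals who complete the intervention".
- **Access.** The website paragraph of section 6.1 says that all data, with email addresses, content ratings, time and log-ins as examples, "will be housed, monitored, and downloaded by the PI from the PI portal within the intervention website". It then says that "Participant data can only be accessed by the specific participant by entering a username and password via the participant login page". Of the PI portal it adds that it "allows PI users access to a real-time view of aggregate data regarding time spent on intervention pages and number of log-ins".
- **Data collected.** Under section 11.2, usage data "will include banner ad click-through rate, time spent on intervention content, and number of intervention website log-ins". Completion of content is not on that list.
- **Linkage.** Section 11.1 keeps identifying, assessment and usage data in separate datasets: "They will be linked only with a randomly generated ID variable that is included in all data".
- **Reminders.** Section 9 sends up to three reminder emails on this condition: "If a participant has not logged into the website within one week of receiving the original email".
- **Skipping.** Section 6.1 lets participants pass over content that makes them uncomfortable. Appendix 3 (D, Website Design) says that finishing a recommended piece moves its tile to a completed row and opens locked content.

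**The concern.** Two sentences in one paragraph appear to give opposite accounts of who can reach the website records. If participant records were truly closed to the study team, and the PI saw only summed page times and log-ins, the share completing the intervention could not be derived. Completion is one of the two results that section 12.3 names for the feasibility of the intervention. Records lost in this way could not be recovered by any rule adopted at analysis. The usage-data list in section 11.2 adds to the doubt because it does not mention completion.

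A second, smaller worry concerns skipping. If a skipped piece does not open the content behind it, a participant who uses the right to skip may lose later material and lower the completion figure for a reason unrelated to poor feasibility.

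**Working it through.** The plan states no completion figure to reproduce, and section 12.3 attaches no target to it. The check has four steps.

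**1. Would summed page time and log-ins be enough?** Inputs: 75 participants in the intervention arm and an upper length of 90 minutes (both section 9), plus an assumed mean of 60 minutes per person.

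- Case A: all 75 finish in 60 minutes with one log-in each. Time 75 × 60 = 4,500 minutes; log-ins 75; completion 75/75 = 100%.
- Case B: 50 finish in 90 minutes, 25 of them with one log-in and 25 with two, and 25 people never log in. Time 50 × 90 = 4,500 minutes; log-ins 25 × 1 + 25 × 2 = 75; completion 50/75 = 67%.

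With *k* pieces of equal length, time per page is 4,500/*k* in both cases. The totals match and completion differs. At other assumed means, case B gives about mean/90: 45/90 = 50%, or 75/90 = 83%. So totals alone do not suffice. A count of completers produced by the site, divided by the number randomized to the arm, would suffice even without individual records. In case B the log-in check behind the section 9 reminders would also single out the 25 who never logged in.

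**2. Are totals all that the study team receives?** No calculation applies, so the places are set side by side.

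| Place | What it implies |
|---|---|
| 6.1, website paragraph, opening statement on data | The PI downloads everything through the portal. The examples include email addresses, which exist only per person, and the list is open-ended |
| 6.1, confidentiality paragraph | The PI retrieves self-report and usage data |
| 6.1, participant log-in sentence | Literally, nobody but the participant |
| 6.1, portal sentence | A live summary view is offered; nothing says that this is the limit |
| 9 | Log-in status is known for each participant |
| 11.1 | Usage data carry an ID; research staff have access to participants' information |
| 11.2 | Authorized study personnel have access |
| Appendix 3, D | Staff can read each participant's comments |

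Only the log-in sentence excludes the study team. The portal sentence is compatible with a download. An ID in the usage data would have no purpose if those data were held only as totals. In a paragraph about encryption and passwords, the log-in sentence is naturally read as saying that one participant cannot open another's account.

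**3. Does the site hold completion?** Yes. The completed row in Appendix 3, and the option in section 9 to resume after logging out, both require stored progress for each participant. Its absence from the list in section 11.2 is an omission from a list, not evidence that the record is missing.

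**4. Is the count defined well enough?** Section 4.2.1 asks for all content, so a skipped piece is not a completed one. Section 9 supplies the rest: 75 planned for the arm, and a request to finish within three weeks of the access email. An analyst would use these without further instruction.

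**The case for a change.** The strongest case for a change runs as follows. The two access sentences cannot both be literally true. Completion is named in no list of collected data, however the word *only* is read. Neither the denominator nor the cut-off is written beside the metric. Access wording also matters as an assurance to minors enrolled under a requested waiver of parental consent. A check of the export before enrolment would be cheap, whereas a missing record could not be rebuilt.

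Much of this stands as description. The sentence is inaccurate as worded, the list is incomplete, and step 1 confirms that totals would not do. What does not stand is the consequence. An uncalculable result needs an export limited to totals, and sections 6.1, 9, 11.1 and 11.2 and Appendix 3 point the other way. Section 11.1 itself says that research staff have access, so the protocol does not hide this. The reminders do not settle the matter either way, because section 9 does not say who sends them and the site could trigger them automatically.

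On skipping, Appendix 3 is silent about what happens after a skipped piece, and its screenshots are not available here; silence is not contradiction. One can attach a size by borrowing the comfort figures in section 6.1. With 3% very uncomfortable and 100% − 90% = 10% outside the comfortable categories, 75 × 0.03 = 2.25 and 75 × 0.10 = 7.5, so about 2 to 8 people would skip something. That would cap completion at 73/75 = 97% to 67/75 = 89%. But those figures come from other research on survey questions, and discomfort is not the same as skipping, so they say little about this intervention.

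**Conclusion.** No change to the plan follows. The participant-only sentence is a clerical slip in a security paragraph, outweighed by the statements elsewhere that give the study team ID-linked data. The missing list entry, the denominator, the three-week cut-off and the treatment of skipped content are gaps with obvious answers in sections 4.2.1 and 9 and Appendix 3. Writing them down would alter no estimate.

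The spread between 67% and 100% in the illustration arises only on the reading that the rest of the document disfavours, so it does not measure a likely error. A request for median page times would be a preference, since section 12.3 plans total time per page.

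The conclusion assumes that the site's stored progress, or at least a count of completers, can be exported. The documents support this but do not state it outright.
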